0	Health Related-Behaviour Fitness (HR-BHF) VAS questionnaire, Self-Reported Questionnaire (Mobile app)	
0	Drug Compliance, Dispense study medication	

Visit 5 (week 8)

0	Symptom Assessment, Vital Parameters		
0	Comprehensive Ayurvedic Evaluation		
0	Medical History, Comprehensive Physical examination		
0	Laboratory work up		
0	Pulse Oximetry		
o	Monitor Adverse Events		
0	Health Related-Behaviour Fitness (HR-BHF) VAS questionnaire, Self-Reported Questionnaire (Mobile app)		
0	Drug Compliance, Dispense study medication		

Visit 6 (Week 12)

Symptom Assessment, Vital Parameters
Comprehensive Ayurvedic Evaluation
Medical History, Comprehensive Physical examination
Laboratory work up
Pulse Oximetry
Monitor Adverse Events

0	o Health Related-Behaviour Fitness (HR-BHI	7) VAS questionnaire, Self-Reported
	Questionnaire (Mobile app)	
0	o Drug Compliance	
0	o Completion Report

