Randomize Eligible Hospitalized Patients (Open Label, Parallel Efficacy, Active Control Standard of Care (SOC), Two Arm Study) Selected Ayurveda Formulation (Adjuvant) Versus SOC (Active Control) Time Points Clinical Assessment Investigations Case Record Form (CRF), Medical Diagnostic (PCR), Serology (IgM, IgG), History Clinical Examination, Ayurveda Baseline Routine Hematology Profile, Special Assessment, Health Status (WHOQs), Assays, X-Ray Chest & Imaging, ECG QoL (HR-BHF) Brief Clin Exam, Ayu Exam, Health Diagnostic (PCR), Serology (IgM, IgG), Week 4 Routine haematology Body Profile, Status (WHO-Qs) & QoL (HR-BHF Qs), Adverse Events (AEs) Special Assays Brief Clin Exam, Ayu Exam, Health Diagnostic (PCR), Serology (IgM, IgG), Week 8 Status (WHO-Qs) & QoL (HR-BHF Routine haematology Body Profile, Qs), Adverse Events (AEs) Special Assays Completion Outcome Assessment, CRF Diagnostic (PCR), Serology (IgM, IgG), Week 12 Clin Exam, Ayu Exam, WHO- Qs & Routine haematology Body Profile, QoL (HR-BHF Qs), AEs Special Assays

*Further Assessment Time Points: (i) During Hospitalization: Daily monitored vital parameters, disease symptoms, disease progression and recovery, and investigations carried out as per protocol till DISCHARGE; Laboratory and Imaging investigations as per protocol but the study investigator and treating physician can do any additional test as per their judgment (ii)Post DISCHARGE: Daily Telephonic Contact using a special mobile phone application for any relapse or any other symptoms or complications or any other Issue (iii) Discharge: Complete all formalities as required for study completion (iv) Skip week 4 or week 8 end point evaluation within 2 weeks of DISCHARGE

The total study period is 12 weeks; Primary Efficacy is 'Clinical Recovery' as described in the protocol; Study participant developing severe COVID 19 or severe complication and requiring special critical support/ ICU/ ventilator support will be withdrawn from the study but followed up to record outcome;

Both Ayurvedic and Allopathic Physicians will jointly examine and monitor study participants in addition to the hospital treating physician

Fig 1: Study Flow Diagram with Schedule of Important Study Events

i. Eligibility:

A) Inclusion Criteria:

- i. Typical clinical presentation of acute onset febrile illness with cough and a RT_PCR based laboratory confirmation test for COVID-19
- ii. Patients with either sex, 18 to 75 years age

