- xiii. Physician decision that involvement in the study is not in the patient's best interest

j. Efficacy:

A) Primary Outcomes:

- a) Mean time (days) for clinical recovery [Day of randomization to the day of clinical recovery (see criteria below)]
- b) Proportion of patients showing 'clinical recovery'

Criteria of 'Clinical Recovery':

- i. Normal body temperature (≤36.6°C axilla or ≤37.2 °C oral)
- ii. Absence of cough or mild cough (infrequent, short episodic, non-wheezy, relieved by minimal or no medication, not interfering with routine speech and not related to lying in bed, mild sore throat or nasal congestion)
- iii. Absence of breathlessness on routine daily self-care chore or respiratory rate less than 30 breaths per minute without supplemental oxygen
- iv. Absence of any other symptom/sign attributed to COVID-19 illness
- v. Normalization of SpO2 by standard peripheral oximetry device (above 95 percent)
- vi. Recovery should be sustained for at least 48 hours under physician observation
- vii. Assessed by physician blinded to treatment allocation (blinded end-point assessment)
- viii. All of the above criteria ought to be fulfilled

Note: Clinical recovery would be deemed from the first day of satisfying the above criteria

B) Secondary Outcomes:

- 1) Rate of patients with negative SARS-CoV-2 on nasal or throat swab in a 2 day continuous real time RT-PCR test beginning from 'first day of clinical recovery' or 'Day 10 after onset of symptoms depending on whichever of the two time points is first achieved
- 2) Timelines (days counted from onset of illness)- normal body temperature, absence or minimal cough (see 'clinical recovery' for the definition), absence of dyspnoea, onset of clinical pneumonia, pneumonia diagnosed on chest X-Ray or CT scan, time to supplemental

oxygen, admit in intensive care unit, mechanical ventilation (non-invasive), mechanical ventilation (invasive), steroid use, respiratory failure, adult respiratory distress syndrome, cytokine storm syndrome, secondary infection, shock, septicaemia shock, hospital discharge, negative nose or throat swab confirmatory test, and all-cause mortality.

- 3) Proportion of patients developing an event that reflects clinical or otherwise improvement of worsening (the events are similar to those listed under Timelines, see above)
- 4) Improvement on pulmonary function tests using simple 'home expiratory spirometer' device and peripheral pulse oximetry

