- 5) Improvement in selected laboratory parameters: blood haemoglobin, differential and total leukocyte counts, liver enzymes, renal functions, acute phase reactants, serum IL-6 and other selected cytokines, serum muscle enzymes (CK, CPK), serum ferritin, serum d-Dimer, anti-oxidant markers, serum BNP (cardiac function)
- 6) Serological Protective Antibody Assay (IgM and IgG)
- 7) Radiological Improvement on digital chest X ray and HRCT chest
- 8) Drug related: side effects and toxicity, and tolerability (Safety criteria: All adverse events occurring during the study will be recorded and monitored as per GCP-ICH guidelines. Safety would also be assessed in case of all withdrawals.)
- 9) Health status: WHO QOL brief, health related behaviour habit and fitness questionnaire based on visual analogue scale

10) Ayurvedic Measures:

BASELINE:

- a) Prakriti
- b) Clinical Features
- c) Ayurvedic Disease Subsets / Stages

FOLLOW UP / MONITORING:

- a) Clinical Features
- b) Ayurveda examination
- c) Ayurvedic Disease Subsets / Stages

k. Medication*:

Interventional Experimental:

i)AYUSH-64: 500 mg tablet, 2 tablets bid (twice daily)

ii) Yashtimadhu: 300 mg tablet, 2 tablets bid (twice daily)

iii)Sanshamani Vati Plus: Each tablet to contain 300 mg Guduchi plus 75 mg Pippali, 2 tablets bid (twice daily) (*Considering the *Dosha* status Ayurveda physician may change the dose.)

Concomitant:

Medication prescribed for other co-existent disease and permitted as per inclusion criteria will continue under medical supervision of the primary care physician and this will be recorded in the CRF.

l. Laboratory investigations:

These are common to the each of the three Ayurveda formulation drug trials:

- i. Haemogram, Platelet count, Total leukocyte differential count, Hemoglobin and ESR,
- ii. Liver function test Serum Bilirubin, ALT, AST, Alkaline phosphatase,
- iii. Kidney Function Test (Serum creatinine, Blood Urea Nitrogen)
- iv. Lipid profile (Total cholesterol, HDL cholesterol, LDL cholesterol, Triglycerides, VLDL)
- v. Blood Sugar Level
- vi. Urine Routine
- vii. C-Reactive protein titer
- viii. LDH, Ferritin
- ix. Pro-Cal
- x. CK, B-type natriuretic peptide (BNP), Troponin, D-Dimer
- xi. Serum Electrolytes (Sodium, Potassium, Chloride, Iron, Zinc, Manganese) Vitamin D, B12
- xii. Oxidation Biomarkers-Superoxide Dismutase (SOD), Glutathoine (GSH)

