- xiii. Cytokine Panel (Interleukin-2, Interleukin 1 4, Interleukin-6, Interleukin-10, TNF-α, Interleukin-1β, Interleukin-13), Monocyte Chemotactic Protein (MCP), Gamma Interferon. RATIONALE FOR CYTOKINE ASSAY: Cytokine assay can be used to study important anti-viral effects (gamma interferon), immune mediated inflammation (IL-6, anti-TNF, IL-17), TH 1 and TH 2 immune response and antibody producing B cell activity (IL4, IL13), activation of immune cells such as macrophage activation (MCP). Intense up regulation and elevation of IL 6 and several other cytokines has been reported by several clinical case series and research in COVID-19 and can guide specific therapy (as in case of use of monoclonal antibody to IL-6 receptor being used to treat Cytokine storm in COVID 19)
- xiv. Serum Immune Response tests (IgG and IgM) for COVID-19
- xv. Urine Pregnancy Test for women of child bearing potential

Other Investigations:

- i. USG Abdomen and Pelvis
- ii. Color Doppler and 12 Lead ECG
- iii. Chest X-ray
- iv. HRCT Chest

m. Withdrawal Criteria

The patient can withdraw at any time during the study without assigning any reason. The investigator may also withdraw the patient due to reasons connected with the severity of disease, interventional drug (adverse event) or some protocol deviation. Detailed description is provided in the protocol.

n. Statistical statement:

The design of the drug trial is exploratory in nature. Though a randomized selection of patients will be done to either of the two arms, the sample size is that of convenience (expert opinion) and the same is not statistically powered however, sample size (70 patients in each arm) sufficient to draw meaningful conclusions. The statistical significance p<0.05(two sided) is predefined for analysis. Statistical analysis will be performed using standard tests to compare the two interventional arms for primary and secondary efficacy measures. Safety events will be also analyzed. Both intent-to-treat and per protocol completer analysis will be performed. Regression analysis will be done to identify predictors of response.

o. Regulatory clearances:

The protocol will be submitted for all regulatory and other relevant approvals including that of the ethics committee prior to beginning the clinical component of the study. The trial protocol will be registered under Clinical Trial Registry of India before enrolling the first patient.

p. Funding agency:

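### Adjunct trials: patients withdrawn on needing critical care would drop out of the planned completer analysis, and their later scheduled assessments are not secured, although ITT can keep them

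*Protocol*

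**What the plan says.** All references are to the adjunct-treatment synopsis in the Protocol.

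- **Fig 1 note.** "Study participant developing severe COVID 19 or severe complication and requiring special critical support/ ICU/ ventilator support will be withdrawn from the study". The sentence does not end there: such a participant "will be withdrawn from the study but followed up to record outcome".
- **Section m, Withdrawal Criteria.** "The investigator may also withdraw the patient due to reasons connected with the severity of disease". This is discretionary and carries no follow-up clause. The section refers to a fuller description that is not in the text at hand.
- **Section n, Statistical statement.** "Both intent-to-treat and per protocol completer analysis will be performed". Neither set is named primary, and neither per protocol nor completer is defined.
- **Section j, Primary Outcomes.** Outcome (b) is the proportion of patients with clinical recovery. No denominator is given.
- **Section j, Secondary Outcomes 2 and 3.** The listed events include "oxygen, admit in intensive care unit, mechanical ventilation (non-invasive), mechanical ventilation (invasive), steroid use, respiratory failure", followed by ARDS, shock and all-cause mortality among others.
- **Fig 1, weeks 4, 8 and 12.** PCR, serology, routine haematology, special assays, health status and quality of life are scheduled.

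**The concern.** The event that triggers withdrawal is one the trial sets out to measure. It appears among the secondary outcomes, and a patient who reaches it is a likely failure on the recovery proportion. Handling it as withdrawal has two consequences.

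First, on the natural reading a patient withdrawn from a 12-week study is not a completer. One of the two planned analyses would then be restricted to patients who did not need critical care, which is a selection made after randomisation on something the adjunct may influence. If the drug works by preventing progression, that analysis cannot show it. With two unranked sets, nothing says which result stands if they disagree. The trials are open label, so discretionary withdrawal for severity could also differ between arms.

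Second, recording outcome is less than continuing the visit schedule. One secondary objective is the effect on surrogate markers of severity, progression and recovery. If patients who needed critical support contribute nothing at weeks 4, 8 and 12, those comparisons lack the patients most informative about progression. No later analysis plan can restore data that were not collected.

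**Working it through.** **Nothing to reproduce.** Section g gives 70 patients per arm. Section n calls this a sample of convenience without statistical powering. No recovery, progression or dropout rate is stated, so every rate below is an assumption.

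**Notation.** Let s be the probability of becoming severe and needing critical support (s_C on standard of care, s_T with the adjunct). Let r be the recovery probability among all other patients, taken as equal in both arms, so the drug acts only by preventing progression. Let q be the probability that a severe patient meets the recovery criteria later within the 12 weeks.

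- ITT recovery in an arm = (1 − s)·r + s·q
- ITT difference = (s_C − s_T)·(r − q)
- Completer recovery in an arm = r, so the completer difference = r − r = 0

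**Simple case.** With 7 of 70 (adjunct) and 14 of 70 (control) severe, r = 1 and q = 0:

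- ITT: (70 − 7)/70 = 63/70 = 90% versus (70 − 14)/70 = 56/70 = 80%, a difference of 10 points.
- Completers: 63/63 = 100% versus 56/56 = 100%, a difference of 0.

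**Range of assumptions.**

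| s_C, s_T | r | q | ITT control | ITT adjunct | ITT difference (points) | Completer difference |
|---|---|---|---|---|---|---|
| 5%, 2% | 0.85 | 0 | 80.75% | 83.30% | 2.55 | 0 |
| 10%, 5% | 0.95 | 0 | 85.50% | 90.25% | 4.75 | 0 |
| 20%, 5% | 0.95 | 0 | 76.00% | 90.25% | 14.25 | 0 |
| 20%, 5% | 1.00 | 0 | 80.00% | 95.00% | 15.00 | 0 |
| 20%, 5% | 0.95 | 0.5 | 86.00% | 92.75% | 6.75 | 0 |
| 20%, 5% | 0.95 | 0.8 | 92.00% | 94.25% | 2.25 | 0 |
| 10%, 5% | 0.95 | 0.8 | 93.50% | 94.25% | 0.75 | 0 |

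The zero in the last column follows from holding r equal in both arms. It shows what the completer set cannot see and does not predict the trial's result. If the adjunct also raised recovery among patients who do not progress, completers would show that part of the benefit and miss the rest. The later-recovery rows show that the ITT difference itself shrinks when severe patients recover within the study.

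**Post-withdrawal data.** The Fig 1 note secures outcome only. It does not say that the week 4, 8 and 12 assessments continue. The recovery criteria in section j also require 48 hours under physician observation and a blinded assessor, and nothing says these apply after withdrawal. A patient who recovers after intensive care may therefore be hard to classify, even under ITT.

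**The case against.** The strongest reply is that the plan already contains the safeguard. Outcome is recorded after withdrawal, and ITT is planned in the same sentence as the completer analysis. Under ITT the denominator stays at 70 per arm and the benefit in the example is fully visible. This stands. A reader might infer that treatment failures leave the trial's recovery proportion and that a real benefit would vanish. The documents do not support that beyond the completer set.

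Other stronger readings also fail:

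- **That every patient who becomes severe is withdrawn.** The Fig 1 note also requires a need for critical, ICU or ventilator support, and section m says only that the investigator may withdraw for severity.
- **That later data come only from patients who did not worsen.** Patients who worsen without needing critical support are outside the Fig 1 rule, and the procedures list daily in-hospital assessments from Day 5 to discharge.
- **That a withdrawn patient is by definition not a completer.** The synopsis gives no definition, and a completion report is listed at discharge as well as at week 12. Exclusion is the natural reading, not a stated rule.

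It is also fair to say that set definitions commonly belong in a statistical analysis plan, that the trials are declared exploratory, that eligibility excludes patients likely to worsen so the numbers may be small, and that some assessments would be impossible in ventilated patients under any wording. These points lower the severity. They do not remove the point, because the synopsis itself fixes withdrawal on an efficacy event and names a completer analysis, and because an analysis plan cannot supply missing visits.

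**Conclusion.** The point holds in limited form. One of two unranked analyses would, on its natural reading, exclude patients because they reached an efficacy failure, and the scheduled assessments of those patients are not secured. The ITT recovery proportion is sound provided outcomes are in fact recorded and classified.

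The size cannot be derived from the documents. On the assumed rates shown, the ITT difference runs from 0.75 to 15 points and the completer difference is 0 throughout, given a drug that acts only by preventing progression. The 10-points-to-0 example further assumes that no severe patient recovers and every other patient does.

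The effect of missing week 4, 8 and 12 data on the secondary comparisons is not quantified here, and the documents do not establish its direction. The point does not address the mean time to recovery. It is worth correcting but not critical in trials declared exploratory.

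**What to change.** 1. **Fig 1 note and section m.** Reconcile withdrawal with the follow-up clause. State that a patient who needs critical support has reached an outcome event and remains in study follow-up to week 12. Collect recovery status, the events in secondary outcomes 2 and 3, and the week 4, 8 and 12 assessments where feasible. Let the same apply to patients whom the investigator withdraws for severity.
2. **Section n, primary set.** Name ITT (all randomised) as primary for the recovery proportion. Count these patients as not recovered unless the recovery criteria are later documented within the 12-week study.
3. **Section n, per-protocol set.** Define it by major protocol deviations rather than by completion, so that an efficacy failure never removes a patient.

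None of this proposes any change to study-drug or clinical-management rules. The cost is wording in three places and a few extra follow-up forms for patients who progress, partly filled from the hospital record.

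### Adjunct trials, primary outcome (a): a plain mean of days to clinical recovery has no value for patients who die, never recover or are lost first, so as written it covers recoverers only

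*Protocol*

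**What the plan says.** All references are to the adjunct-treatment synopsis in the Protocol, which serves three separate two-arm drug trials of 70 patients per arm.

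- Section j, A) Primary Outcomes, item a): "Mean time (days) for clinical recovery [Day of randomization to the day of clinical recovery (see criteria below".
- Same section, item b): "Proportion of patients showing 'clinical recovery", with no day attached.
- Same section, on dating the event: "Clinical recovery would be deemed from the first day of satisfying the above criteria". One of the criteria is: "Recovery should be sustained for at least 48 hours under physician observation".
- Fig 1 notes, on participants who become severe and need critical support: they "will be withdrawn from the study but followed up to record outcome".
- Section m, Withdrawal Criteria: "The investigator may also withdraw the patient due to reasons connected with the severity of disease, interventional drug (adverse event) or some protocol deviation".
- Section n, Statistical statement: "Both intent-to-treat and per protocol completer analysis will be performed". The significance level is 0.05 two-sided, and the tests are described only as standard ones.

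Death, intensive care and ventilation appear among the secondary timelines and events in section j. Nothing links them to item a).

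**The concern.** A mean of days to an event needs a day for every patient who enters it. Patients who die, who never satisfy all the recovery criteria, or who are lost before doing so have none, and the synopsis gives no censoring rule, substitute value or competing-event rule for them. A plain mean is then computed on those who recovered.

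The recoverers in the two arms are not randomised groups, because treatment may affect who recovers. An add-on that brings some slow patients to a late recovery adds long times to its own mean. An add-on that turns late recoverers into non-recoverers removes long times and looks faster. The comparison also leaves out some randomised patients, which an intent-to-treat analysis should not do. At stake is the direction, or at least the size, of the effect on a primary outcome in all three trials.

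**Working it through.** The synopsis states no effect size, standard deviation, recovery rate or dropout rate, and it describes the sample size as one of convenience. There is no planned figure to reproduce. From the protocol come 70 per arm and the definition of the outcome. Every rate and recovery time below is an assumption, as is the day-28 cap.

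**1. Can the sign reverse?** Assume that 90% of controls recover at a mean of 8 days and 10% never recover. The add-on rescues half of the non-recoverers, who recover at day 20, and changes nobody else.

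- Recoverer mean, control: 8.00 days.
- Recoverer mean, add-on: (0.90 × 8 + 0.05 × 20) / 0.95 = 8.20 / 0.95 = 8.63 days. Apparent harm: 0.63 day.
- Mean capped at day 28, control: 0.90 × 8 + 0.10 × 28 = 10.0 days.
- Mean capped at day 28, add-on: 0.90 × 8 + 0.05 × 20 + 0.05 × 28 = 9.6 days. Actual benefit: 0.4 day.

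With the arms exchanged, a drug that turns 5% of patients from late recoverers into non-recoverers looks 0.63 day faster.

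**2. When does it reverse?** Let k of 70 controls never recover and the rest recover at mean m = 8. In the add-on arm the ordinary recoverers are d days faster, and all k others recover at day L. The recoverers-only difference (add-on minus control) is

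[(70 − k)(m − d) + kL] / 70 − m,

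which is positive, the wrong sign, when d < k(L − m) / (70 − k). The table gives that threshold for d, in days.

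| k of 70 | L = 14 | L = 20 | L = 28 |
|---|---|---|---|
| 2 (3%) | 0.18 | 0.35 | 0.59 |
| 4 (6%) | 0.36 | 0.73 | 1.21 |
| 7 (10%) | 0.67 | 1.33 | 2.22 |
| 10 (14%) | 1.00 | 2.00 | 3.33 |
| 14 (20%) | 1.50 | 3.00 | 5.00 |

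Two worked cases with d = 1 and L = 20, where every add-on patient does better:

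- k = 10: the recoverer difference is (60 × 7 + 10 × 20) / 70 − 8 = +0.86 day. With all 70 counted and a day-28 cap, it is 8.86 − (60 × 8 + 10 × 28) / 70 = 8.86 − 10.86 = −2.00 days.
- k = 2: the recoverer difference is (68 × 7 + 2 × 20) / 70 − 8 = −0.63 day. With all 70 counted, it is 7.37 − (68 × 8 + 2 × 28) / 70 = 7.37 − 8.57 = −1.20 days. The sign is right, but the effect is diluted.

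**3. How often in trials of this size?** Simulation of 5,000 trials per row, 70 per arm, lognormal times with mean 8 and SD 4, d = 1, rescued patients recovering at day 20.

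| Non-recovery, control vs add-on | Recoverers only: mean difference (days) | Wrong sign | All patients, day-28 cap: mean difference (days) | Wrong sign |
|---|---|---|---|---|
| 15% vs 5% | +0.36 | 68% | −1.66 | 9% |
| 10% vs 5% | −0.32 | 34% | −1.29 | 12% |
| 5% vs 2% | −0.60 | 20% | −1.18 | 10% |
| 2% vs 1% | −0.86 | 9% | −1.06 | 8% |

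**The case against.** The best defence is that the text is incomplete rather than wrong. It nowhere says that only recoverers are averaged; it promises an intent-to-treat analysis; and a statistical analysis plan that is not shown could supply a censoring or worst-value rule. A restricted mean is itself a mean time in days. This is fair as far as it goes: averaging over recoverers is the natural reading of the item, not its stated text. But the protocol itself fixes the summary as a mean to the day of recovery, and that definition gives some randomised patients no value.

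Three stronger readings are tempting, and the documents do not support them.

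- A reader might infer that everyone who worsens or is withdrawn lacks a value. The Fig 1 notes keep severe withdrawals under follow-up for outcome, so those who later recover can be dated. What is not stated is whether that follow-up applies the blinded, 48-hour criteria.
- A reader might infer that the sign will usually reverse. That needs non-recovery rates and late recovery times that the protocol does not give. Excluding severe disease and patients expected to worsen points to few non-recoverers, where dilution is the usual result.
- A reader might infer that primary (b) is useless because nearly everyone will have recovered by week 12. The protocol does not say that (b) is read at week 12, and (b) does count non-recoverers. Even at 90% against 100% recovery, 70 per arm gives about 71% power by Fisher's exact test and 93% by uncorrected chi-square. At 95% against 100% the figures are 14% and 47%.

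Primary (b) and the secondary events would also expose a drug that prevents recovery. That limits the damage, but no rule says which primary governs if (a) and (b) disagree. Finally, the trials are labelled exploratory and unpowered. That lowers the stakes, yet section n still predefines a significance level and expects useful conclusions from this sample.

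**Conclusion.** The point holds in a limited form. Taken as written, primary (a) is undefined for patients who die, never recover or are lost before recovery, and a plain mean conditions on recovery. The size rests wholly on assumed rates. At about 10% to 15% non-recovery in controls with late rescue, a real benefit can appear as harm. With 2 to 4 non-recoverers of 70, rescue at day 20 and a control mean of 8 days, reversal needs a speed-up in the ordinary recoverers below about 0.35 to 0.73 day. Otherwise the benefit is understated. The missing day for (b) is a smaller gap of the same kind. Both should be fixed before any comparison is made. Neither shows that the trials cannot answer their question.

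**What to change.** Replace the mean in (a) with time from randomisation to clinical recovery in all randomised patients. Compare the arms by log-rank with cumulative incidence, or by restricted mean time, to one prespecified horizon. Day 28 above is only an illustration; the sponsor should choose the horizon.

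State how each kind of patient enters:

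- Deaths, and severe withdrawals who do not later recover, count as not recovered up to the horizon.
- Severe withdrawals who later recover count at their recovery date, taken from the follow-up already promised.
- Only true loss to follow-up is censored.

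Give primary (b) a fixed day from randomisation, also chosen by the sponsor.

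The cost is statistical wording, plus making sure that follow-up of withdrawn patients records a recovery date under the same criteria. No change to sample size or treatment is needed, and in-hospital patients are already assessed daily.

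### Adjunct trials: primary outcome (a) is a plain mean of days to recovery, undefined for patients with no observed recovery, so unequal non-recovery between arms can bias it

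*Protocol*

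**What the plan says.** All references are to the adjunct-treatment synopsis in the protocol.

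- **Section j, A) Primary Outcomes.** Outcome (a) is "Mean time (days) for clinical recovery [Day of randomization to the day of clinical recovery". Outcome (b) is "Proportion of patients showing 'clinical recovery", with no time point attached.
- **Criteria of clinical recovery, same section.** Every criterion must be met, and "Recovery should be sustained for at least 48 hours under physician observation".
- **Section j, B) Secondary Outcomes, item 2.** The listed events include "negative nose or throat swab confirmatory test, and all-cause mortality", so deaths are anticipated.
- **Notes to Fig 1.** A participant who becomes severe or needs critical support "will be withdrawn from the study but followed up to record outcome".
- **Section m, Withdrawal Criteria.** "The patient can withdraw at any time during the study without assigning any reason". Also, "The investigator may also withdraw the patient due to reasons connected with the severity of disease".
- **Section n, Statistical statement.** Unnamed standard tests are planned at two-sided p<0.05, with both an intention-to-treat and a per-protocol completer analysis. The 70 patients per arm are a convenience number without a power calculation.

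The synopsis gives outcome (a) no horizon and no value for a patient without a recovery day.

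**The concern.** Outcome (a) fixes both the variable (days to the recovery day) and the summary (a mean). The variable does not exist for a patient who never recovers or whose recovery is not observed, so an arithmetic mean can include only the others. Who those others are is decided after randomisation and may depend on treatment. Investigator withdrawal for disease severity links at least some of the missing days to prognosis.

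Suppose a drug turns some non-recoverers into late recoverers. Their long times enter the drug arm's mean, while their counterparts on standard of care drop out of theirs. The drug can then look slower although more patients recover. Intention to treat does not cure this, because a randomised patient with no recovery day still contributes no number. The same outcome definition serves three separate drug trials.

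**Working it through.** **Inputs from the protocol.** 70 patients per arm and 12 weeks (84 days) of follow-up. It gives no recovery rate, mean, SD or effect, so there is no stated figure to reproduce. Every rate and day below is an assumption, including the 28-day horizon.

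**Formulas.** Let group k be a share p_k of the arm recovering at mean day d_k.
- Mean among recoverers = Σ p_k d_k / Σ p_k.
- Mean over all patients to horizon H = Σ p_k d_k + (1 − Σ p_k) × H.

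**Example 1.** On standard of care (SOC), 90% recover at mean day 9 and 10% never do. On drug, half of those failures recover at day 20 and nobody else changes.
- Recoverers: SOC 9.00; drug (0.90×9 + 0.05×20)/0.95 = 9.10/0.95 = 9.58. The drug looks 0.6 day slower.
- All patients, H = 28: SOC 0.90×9 + 0.10×28 = 10.9; drug 0.90×9 + 0.05×20 + 0.05×28 = 10.5. The drug is 0.4 day better.
- Late recovery at day 25: (8.10 + 1.25)/0.95 = 9.84, or +0.8 day among recoverers.
- Failures 15% v 5%: (0.85×9 + 0.10×20)/0.95 = 10.16, or +1.2 days among recoverers.

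**Example 2, whole patients.** On SOC, 56 of 70 recover at mean day 8. On drug, the same 56 do so and 7 more recover at day 21.
- Recoverers: 8.00 v (56×8 + 7×21)/63 = 595/63 = 9.44.
- All 70, H = 28: (448 + 14×28)/70 = 12.0 v (595 + 7×28)/70 = 11.3.
- All 70, H = 84: (448 + 14×84)/70 = 23.2 v (595 + 7×84)/70 = 16.9.

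**Break-even for Example 1.** Solve (0.90m + 0.05×20)/0.95 = 9. Then m = (8.55 − 1.00)/0.90 = 8.39. If the drug also shortens the other patients' recovery by about 0.6 day, the reversal is gone.

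**Grid at 70 per arm.** SOC recovery 80–95% at mean day 8, 5 or 10 points more on drug, extra recoverers at day 14, 21 or 28.
- No change in the other patients: the recoverer mean is longer on drug in all 21 cases, by 0.27 to 2.22 days.
- Other patients 0.5 day faster: the difference runs from −0.20 to +1.78 days, and the reversal persists in 17 of 21 cases.

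**Simulation.** 3,000 trials of 70 v 70; lognormal recovery times with median 8 days; the patients with the worst prognosis leave unrecovered; Welch t-test on recoverers.

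| Unrecovered, SOC v drug | Speed-up on drug | Recoverer mean, drug − SOC (days) | Drug looks slower | Significantly slower | 28-day mean over all patients favours drug |
|---|---|---|---|---|---|
| 5% v 5% | none | −0.01 | 49.4% | 2.3% | 51.8% |
| 10% v 5% | none | +0.36 | 70.1% | 7.7% | 72.9% |
| 15% v 5% | none | +0.67 | 84.4% | 16.9% | 87.9% |
| 20% v 5% | none | +0.95 | 91.9% | 29.6% | 96.3% |
| 10% v 5% | about 5% | −0.07 | 45.8% | 1.7% | 84.5% |
| 15% v 5% | about 5% | +0.22 | 62.9% | 4.7% | 94.7% |
| 20% v 5% | about 18% | −0.64 | 13.3% | 0.2% | 99.9% |

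**Outcome (b) at 70 per arm.** Power is 38% for 80% v 90%, 51% for 85% v 95% and 77% for 80% v 95%.

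**The case against.** *The handling may be settled elsewhere.* No sentence restricts the analysis to recoverers, and the statistical analysis plan is not shown. Intention to treat is planned, and a log-rank test would fit the phrase about standard tests. This stands in part: averaging over recoverers is the literal consequence of the outcome as named, not a stated rule. But a later plan could repair it only by redefining the primary outcome fixed here, so this is more than missing detail.

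*Outcome (b) counts non-recoverers.* In Example 1 it would read 90% v 95% in the drug's favour. That stands and limits the harm. It does not remove it: (b) has no time point, its power is limited for most such differences, and nothing says what is concluded if (a) and (b) point in opposite directions.

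*The size is assumed.* Eligibility is limited to mild to moderate disease and excludes patients likely to worsen, so non-recovery may be small. Example 1 at 70 per arm is 7 v 3.5 failures. That the extra recoverers are late is also an assumption. All of this stands.

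A reader might go further in two ways that the documents do not support:
- *Every withdrawn patient lacks a value.* The Fig 1 notes provide outcome follow-up for patients withdrawn as severe, so a later recovery could be dated, and a patient who recovered before leaving already has a day.
- *The secondary timelines share the fault to the same degree.* Times to events such as "respiratory failure, adult respiratory distress syndrome, cytokine storm syndrome, secondary infection, shock, septicaemia shock, hospital discharge" do exist only for patients with the event. But no mean is specified there, and secondary item 3 compares the proportions with similar events. Nor does this point justify moving their time origin from illness onset.

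**Conclusion.** The point holds as a badly fixed summary measure. Outcome (a) has no value for patients who die, never recover, or leave before recovery is observed, and the synopsis anticipates such patients.

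The direction and size of the bias cannot be read from the protocol. Under the assumed rates, with no acceleration in other patients, the recoverer mean is about 0.3 to 2.2 days longer on a drug that helps more patients recover. A reader might infer that reversal is to be expected. It is only possible: it needs unequal non-recovery, late recovery among the extra recoverers, and little acceleration in the rest. With equal non-recovery there is no bias, and an 18% speed-up removes the reversal even at 20% v 5%.

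Should-fix rather than must-fix: the trials are declared exploratory, (b) gives a partial check, and no non-recovery rate is given. It still matters, because the statistical statement sets a significance level and expects 70 per arm to support meaningful conclusions.

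**What to change.** - Redefine (a) as time from randomisation to clinical recovery in all randomised patients, analysed by cumulative incidence of recovery (Kaplan-Meier and log-rank) up to a fixed horizon within the 12 weeks, chosen before the data are compared by arm.
- Keep deaths, and severe withdrawals who do not recover, as not recovered to that horizon. Do not censor them at death or withdrawal.
- Date later recoveries of withdrawn patients from the outcome follow-up already planned. Censor only true losses to follow-up.
- Report the median, or the restricted mean difference to the horizon, in place of the raw mean.
- Give (b) the same horizon, and state how the two primary outcomes are read if they disagree.

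The cost is outcome wording, plus recording a recovery date for withdrawn patients, since the Fig 1 notes promise only that the outcome is recorded. A plain mean in days is given up for a median or restricted mean. The secondary timelines can keep their present origin.
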